9.4.2. Primary efficacy analysis

The PaO₂/FiO₂ ratio will be analyzed separately, at the two time points: 0 hours (ICU admission) and 24 hours after ICU admission. Analysis of variance will be used, including terms for treatment and center. The importance of the treatment by center interaction will be investigated but if this is not significant at the 10% level, this term will be excluded from the final model. If a center by treatment interaction is detected, alternative methods of presentation will be explored. Treatment effect will be primarily compared using a one-sided 0.05 level test and then re-tested for consistency with a two-sided 0.05 level test. Type of transplant (single or bilateral) will then be included in the model of the analysis to explore any possible, even unanticipated, differences due to the specific procedure.

Primarily the data will be analyzed excluding missing data. As confirmatory analysis, the ANOVAs will be performed substituting any missing values by the last observation carried forward (LOCF) method, in patients extubated before 24 hours. If the data are missing due to

patient death, the PaO₂/FiO₂ ratio will be given a zero value. If the data are missing due to lack of recording while on mechanical ventilation, these data will not be substituted.

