### 3.2 Sample Size Considerations

Under the following assumptions:

1. A single primary endpoint –  $\text{PaO}_2/\text{FiO}_2$  ratio
2. One primary comparison: repertaxin versus placebo at 24 hours post ICU admission ( $H_0: \mu_R = \mu_P$ ;  $H_1: \mu_R > \mu_P$ ).
3. A one-sided two group t-test of statistical significance
4.  $\alpha$ -level or probability of Type I error associated with the test of 0.05
5. A placebo mean of 315 mmHg
6. A common standard deviation of 137 mmHg
7. A sample size of 50 in each group

the study has 81% power to detect a difference in means of 70 mmHg ( $\mu_R = 385$  mmHg) and 56% power to detect a difference in means of 50 mmHg ( $\mu_R = 365$  mmHg). The data for assumptions 5 and 6 is taken from the results of 700 lung transplant operations at the Washington University. However, there are currently no data available to provide an estimate of the treatment effect size for this study.

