#### Primary analysis

The ratio at the two time points will be analyzed using a repeated measurements model using PROC MIXED within SAS®. The model will include fixed effect terms for center, time point and treatment. Time point will be specified as a repeated measurement. In order to select an appropriate matrix for the observations within each patient, 3 models will be fitted using the compound symmetry, Huynh-Feldt and unstructured structures. The matrix for the final model will be selected using Akaike's Information Criterion where the lowest value indicates the best fit. Type III sums of squares from the mixed procedure within SAS® will be used to assess the significance of individual terms within the model using the selected matrix structure. The importance of the treatment-by-center interaction will be investigated but if the term is not significant at the 10% level, it will be excluded from subsequent models. If there are insufficient data within each center and treatment combination to allow estimation of effects, centers will be pooled based on similar surgical practices.

The adjusted least squares means will be estimated for each combination of time point and treatment. The treatment effect within each time point will be compared using a one sided test at the 5% level. Missing data will be excluded. The primary analysis will be performed for the ITT population.

The tests of the fixed effects will be presented, together with the estimated least squares means and summary statistics of the raw PaO2/FiO2 ratio for each of the two treatments at each time point. The estimated treatment difference between repertaxin and placebo at each time point will be presented together with the corresponding 95% confidence interval. The confidence interval will be generated using  $\alpha=0.10$  and the lower limit will be replaced by  $-\infty$ .

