#### Sensitivity Analyses

The primary analysis will be repeated using the PP population.

The primary analysis will be repeated using a two-sided test at the 5% level.

The primary analysis will be repeated using the last observation carried forward (LOCF) method to substitute a missing PaO2/FiO2 ratio for patients extubated within 24 hours after ICU submission. For patients who died within 24 hours of ICU admission a ratio of 0 will be used at the 24 hour time point. Data for patients with a ratio missing for any other reason will not be substituted.

The primary analysis will be performed including the type of transplant (single or double) as a fixed effect covariate whose importance will be assessed at the 5% level. The interaction term for type of transplant and treatment will also be fitted but if this is not significant at the 10% level it will be excluded from the final model. The randomization has not been stratified by the type of transplant and therefore this analysis will only be performed if there are sufficient data within each treatment, center and type of transplant combination.

In summary, the following presentations of PaO2/FiO2 ratio at time 0 and 24 hours will be produced:

Repeated Measurements Analysis using a one-sided test for the ITT population with missing data excluded.

Repeated Measurements Analysis using a one-sided test for the PP population with missing data excluded.

Repeated Measurements Analysis using a two-sided test for the ITT population with missing data excluded.

Repeated Measurements Analysis using a one-sided test for the ITT population with substitution of missing data.

Repeated Measurements Analysis using a one-sided test for the ITT population including type of transplant but with missing data excluded.

Repeated Measurements Analysis using a one-sided test for the PP population including type of transplant but with missing data excluded.

Additional exploratory analyses may be performed to further investigate the robustness of the primary efficacy data.

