## 9.5.2 Secondary Variables

### 9.5.2.1 PaO2/FiO2 ratio at 48 hours and 72 hours after ICU admission

These data will be analyzed as described for the primary analysis using a one-sided test at the 5% level and with missing data excluded. A further analysis including type of transplant again using a one-sided test at the 5% level and with missing data excluded will also be performed provided there are sufficient data recorded. Both these analyses will be performed on the ITT and PP analysis populations.

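### SAP 9.5.1 promises a treatment test at each of 0 h and 24 h, but the listed model has no treatment-by-time term and can give only one common effect

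*SAP*

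**What the plan says.** The mean model in SAP 9.5.1 (Primary analysis) is given in one sentence: "The model will include fixed effect terms for center, time point and treatment". A treatment-by-center term is also tried, and dropped if it is not significant at the 10% level. Time point is the repeated factor. One of three within-patient covariance matrices is chosen by AIC.

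The outputs described in the same section are specific to time:

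- On the test: "The treatment effect within each time point will be compared using a one sided test at the 5% level"
- On the estimate and its interval: "The estimated treatment difference between repertaxin and placebo at each time point will be presented together with the corresponding 95% confidence interval"
- On the cell means: "The adjusted least squares means will be estimated for each combination of time point and treatment"

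The shell for Tables 2.1.x and 2.2.x (SAP 13) has fixed-effect rows for center, time, treatment and center-by-treatment, and separate comparison rows for 0 h and 24 h.

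The only other interaction in the efficacy models is in the sensitivity analyses: "The interaction term for type of transplant and treatment will also be fitted". For 48 h and 72 h, SAP 9.5.2.1 reuses the model: "These data will be analyzed as described for the primary analysis using a one-sided test at the 5% level and with missing data excluded".

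Two other places bear on the point. SAP 3.2 bases its power on "One primary comparison: repertaxin versus placebo at 24 hours post ICU admission". Protocol 9.4.2 says that the ratio "will be analyzed separately, at the two time points: 0 hours (ICU admission) and 24 hours after ICU admission". SAP 1.2 records no change from the protocol.

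**The concern.** A model with main effects of center, time and treatment assumes that the treatment effect is the same at 0 h and 24 h. It cannot produce the two time-specific contrasts that the section asks for. A programmer who follows the model sentence would print a pooled 0 h/24 h effect in a row labelled 24 h.

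An effect present only at 24 h would be diluted. An effect present only at 0 h would appear as a 24 h effect. SAP 9.5.1 also waives multiplicity adjustment partly because the contrasts come from this model, so its form matters there too. The protocol's separate analyses would have given time-specific effects.

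**Working it through.** **The plan's own figure.** Inputs from SAP 3.2: 50 per group, SD 137, one-sided 5%, differences of 70 and 50 mmHg. The standard error (SE) is 137 × √(2/50) = 27.4. The noncentrality is 70/27.4 = 2.555 or 50/27.4 = 1.825. The noncentral t with 98 df gives 81.4% and 56.7%, against the stated 81% and 56%. The power figure is sound for a contrast at one time point.

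**The structure.** As listed, E(Y) = μ + center + time + treatment, so repertaxin minus placebo contains no time parameter. It is the same at 0 h and 24 h under any covariance matrix. Treatment-by-center, if kept, lets the effect differ by center but not by time. As a check, the listed model was fitted to one simulated data set (true effects 0 and 70 mmHg, 8 centers). It gave least squares mean differences of 24.33 at 0 h and 24.33 at 24 h. With treatment-by-time added they were 0.20 and 48.46.

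**What the common effect estimates.** Inputs: 50 per arm; SDs of 137 at both times (SAP 3.2), or 137 at 0 h and 117 at 24 h (protocol 9.1). Assumptions: complete data and within-patient correlation ρ of 0.3, 0.5 or 0.7, which the documents do not give. With SDs s₀ and s₂₄, generalized least squares gives

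- 24 h weight: w = (s₀² − ρs₀s₂₄) / (s₀² + s₂₄² − 2ρs₀s₂₄)
- common effect: (1 − w)·δ₀ + w·δ₂₄
- SE² = (2/50) · s₀²s₂₄²(1 − ρ²) / (s₀² + s₂₄² − 2ρs₀s₂₄)
- power: Φ(effect/SE − 1.645)

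With two time points, Huynh-Feldt and unstructured are the same three-parameter matrix, so only two weightings can arise: this one, and equal weights under compound symmetry.

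Example, SDs 137/117 and ρ = 0.5: the covariance is 0.5 × 137 × 117 = 8,014.5. Then w = (18,769 − 8,014.5)/(18,769 + 13,689 − 16,029) = 10,754.5/16,429 = 0.655. With δ = (0, 70) the estimate is 0.655 × 70 = 45.8 mmHg, the SE is 21.7 and the power is 0.681.

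Results for ρ = 0.3 / 0.5 / 0.7 (probability that the common effect is significant, one-sided 5%):

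| Case | 24 h weight | SE | True effects (0, 70) | True effects (70, 0) |
|---|---|---|---|---|
| SD 137 at both times | 0.50 | 22.1 / 23.7 / 25.3 | 35 mmHg; 0.476 / 0.433 / 0.398 | 35 mmHg; 0.476 / 0.433 / 0.398 |
| SDs 137/117, unstructured | 0.611 / 0.655 / 0.754 | 20.2 / 21.7 / 22.9 | 42.8 / 45.8 / 52.7 mmHg; 0.681 / 0.681 / 0.746 | 27.2 / 24.2 / 17.3 mmHg; 0.382 / 0.299 / 0.187 |
| SDs 137/117, compound symmetry | 0.50 | 20.5 / 22.0 / 23.4 | 35 mmHg; 0.524 / 0.478 / 0.440 | 35 mmHg; 0.524 / 0.478 / 0.440 |

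A contrast specific to 24 h has SE 27.4 and power 0.819 for 70 mmHg (SD 137), or SE 23.4 and power 0.911 (SD 117). When there is no 24 h effect it rejects 5% of the time.

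If the true effect is 70 mmHg at both times, the additive model is unbiased and has power 0.936 / 0.904 / 0.870 against 0.819 (SD 137), or 0.965 / 0.944 / 0.922 against 0.911 (SDs 137/117, unstructured).

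**Simulation.** With 8 centers in the model (1,000 trials per case, known covariance) and true effects (0, 70), the listed model rejected in 63% to 72% of trials (SDs 137/117) or 39% to 46% (SD 137). With treatment-by-time added, the 24 h contrast rejected in 87% to 89% or 79% to 81%, and the 0 h contrast in about 4% to 6%.

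**The case against.** The intent is fairly clear. Three sentences in SAP 9.5.1 and both comparison rows of the shell require time-specific results, and SAP 1.1 says to read the SAP with the protocol, which analyzes the time points separately. The model sentence is not exhaustive, since treatment-by-center is named only later. The shell is generic: it has no row for type of transplant, although some of the tables it covers add that term, and it shows only 0 h and 24 h although it also covers 48/72 h. A missing row is therefore weak evidence of exclusion. SAP 10 requires independent programming, and two identical comparison rows would be conspicuous. Raw means by arm and time are tabulated, and the SAP calls the study non-pivotal.

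Most of this stands. It makes an undetected error less likely, but it does not supply the term. Treatment-by-center and treatment-by-transplant type are each named and given a retention rule. Treatment-by-time has neither, so a programmer who adds it cannot tell whether to keep it when it is not significant. Two independent programmers may follow the same sentence, and a check against the plan cannot settle a point on which the plan supports both models.

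The patterns (0, 70) and (70, 0) are extremes chosen to show the mechanism. The documents do not predict either.

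**Conclusion.** The concern holds. As listed, the primary model yields one treatment effect shown twice. This follows from the model's form and needs no assumption. Read literally, the plan contains no test or interval specific to 24 h; read by its promised outputs, it needs a term that it never states.

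The size of the distortion does rest on assumptions: complete data, ρ of 0.3 to 0.7, and effects that differ between the times. For an effect of 70 mmHg at 24 h only, power falls from 82% to 40%–48% (SD 137), or from 91% to 68%–75% (SDs 137/117, unstructured) or 44%–52% (compound symmetry). For an effect at 0 h only, the 24 h row is significant in 40%–48%, 19%–38% or 44%–52% of trials in the same three cases, instead of 5%. If the effect is equal at both times there is no bias and a gain in power, but the SAP neither states nor tests that equality.

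This has to be settled before unblinding. Otherwise the choice between two models for the primary result could be made with the data in view.

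**What to change.** In SAP 9.5.1, list the fixed effects as center, time point, treatment and treatment-by-time point. State that the interaction is kept whatever its p-value, and that the 0 h and 24 h contrasts are taken from it. Add its row to the shell for Tables 2.1.x and 2.2.x, and make the same change for 48/72 h in SAP 9.5.2.1. In SAP 1.2, record the move from the protocol's separate ANOVAs to a repeated-measures model; that entry is needed even once the term is added. The alternative is to return to the separate ANOVAs of protocol 9.4.2.

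The cost is one degree of freedom, one shell row and some wording, with no new data. The SE of the 24 h contrast is 2% to 16% (SDs 137/117, unstructured) or 8% to 24% (SD 137) larger than that of the pooled effect, so some power is lost if the effect really is equal at both times. The ratio is measured only during mechanical ventilation, so 24 h values will be missing after early extubation. If 20% were missing at random (an assumed figure), the penalty would be 5% to 22% or 13% to 33%. That is the price of a contrast specific to 24 h, which is what SAP 3.2 powers.

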9. STATISTICAL ISSUES

9.1. SAMPLE SIZE

The sample size has been estimated based on PaO₂/FiO₂ ratios immediately and at 24 hours from the results of 700 lung transplant operations at the Washington University. The database reports means and standard deviations for this endpoint of 329±137 mmHg at the initial ICU assessment and 315±117 mmHg at 24 hours.

A sample size of 50 in each group will have a 81% power to detect a difference in means of 70 mmHg (the difference between a placebo mean of 315 and a treated mean of 385, a 22% improvement) assuming that the common standard deviation is 137 using a two group t-test with a 0.05 one-sided significance level. Alternatively, a sample size of 50 in each group will have a 56% power to detect a difference in means of 50 mmHg (the difference between a placebo mean of 315 and a treated mean of 365, a 15% improvement) assuming that the common standard deviation is 137 using a two group t-test with a 0.05 one-sided significance level.

There is no currently available data to provide a knowledgeable estimate of the effect size in this study. If the effect size is smaller than 15%, the power of this study will be reduced and the chance of a Type II error is increased. Under such circumstances, this study would still provide valuable data regarding the effect size in the primary outcome variable as well as the results in all of the secondary, exploratory endpoints and subgroup analysis.

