### 1.3 Changes from previous versions of SAP

For the primary analysis, the covariance matrix for the final model was wrongly defined as the matrix with the highest value for the Akaike's Information Criterion. The selection criterion has been changed to the matrix with the lowest value for the Akaike's Information Criterion.

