### 9.5 Efficacy analyses

### 9.5.1 Primary Variable

The PaO2/FiO2 ratio will be analyzed at two time points: 0 hours (time of ICU admission) and 24 hours after ICU admission. These analyses will be performed using both the ITT and PP populations with the ITT analysis considered as the primary result. As this is not a pivotal study and the contrast estimates will be obtained from a repeated measurements model fitted for data at both time points, adjustments for multiplicity are not considered necessary.

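### With two time points, the AIC step in the primary model only decides whether equal SDs are imposed at 0 h and 24 h. Prespecifying the unstructured matrix is a small improvement at almost no cost.

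*SAP*

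**What the plan says.** SAP 9.5.1 states that the PaO2/FiO2 ratio "will be analyzed at two time points: 0 hours (time of ICU admission) and 24 hours after ICU admission". Under Primary analysis it specifies a repeated measurements model: "The model will include fixed effect terms for center, time point and treatment". For the within-patient covariance, "3 models will be fitted using the compound symmetry, Huynh-Feldt and unstructured structures", and then "The matrix for the final model will be selected using Akaike's Information Criterion where the lowest value indicates the best fit".

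Inference is per time point: "The treatment effect within each time point will be compared using a one sided test at the 5% level". The table shell in SAP 13 has a separate difference, standard error, confidence interval and p-value at 0 h and at 24 h. Its list of fixed effects has center, time, treatment and center-by-treatment, but no time-by-treatment term.

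The planning data in Protocol 9.1 are "329±137 mmHg at the initial ICU assessment and 315±117 mmHg at 24 hours", from 700 operations. The power calculation uses a common SD of 137 mmHg. Protocol 9.4.2 planned a separate ANOVA at each time point, which leaves each time with its own residual variance. SAP 1.2 lists no changes from the protocol.

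**The concern.** The plan appears to compare three candidate structures, but with two time points there are only two distinct ones. Compound symmetry gives both per-time contrasts one averaged variance. If the true SD is larger at ICU admission than at 24 h, as the planning data suggest, that averaging makes the standard error too small at 0 h and too large at 24 h, the time point that SAP 3.2 names for the power calculation. The data would decide whether this happens, and the protocol's separate ANOVAs never assumed equal variances. At stake are the accuracy of the one-sided error at each time and a little power at 24 h.

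**Working it through.** **Inputs from the documents.** 50 per arm, one-sided 5%, differences of 70 and 50 mmHg, common SD 137 (SAP 3.2); SDs 137 and 117 (Protocol 9.1); 8 centers (SAP 3.3). **Assumed, not in the documents:** within-patient correlation 0.3, 0.5 or 0.7; complete data; a time-by-treatment term in the model.

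**1. The plan's own power.** SE = 137 × √(2/50) = 27.4 mmHg. A noncentral t with 98 df gives 81.4% for 70 mmHg and 56.6% for 50 mmHg, against the stated 81% and 56%. The stated figures are reproduced.

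**2. Huynh-Feldt equals unstructured.** Huynh-Feldt has variances v0 and v24 and sets the covariance to (v0 + v24)/2 − λ. With two times, λ is free to give any covariance, so three parameters describe every 2×2 matrix, exactly as unstructured does. Numerical REML fits gave identical AICs (238.134 for both in one model, 241.123 for both in another). The tie is harmless because either choice gives the same results. What remains is compound symmetry (two parameters) against unstructured (three).

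**3. Upper bound on the effect, if compound symmetry were always imposed.** Variance ratio = 137²/117² = 18769/13689 = 1.37. Pooled SD = √[(18769 + 13689)/2] = 127.4. Per-time SEs for 50 per arm:

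- Unstructured: 137 × 0.2 = 27.4 at 0 h; 117 × 0.2 = 23.4 at 24 h.
- Compound symmetry: 127.4 × 0.2 = 25.5 at both.
- Ratios: 25.48/27.4 = 0.93 and 25.48/23.4 = 1.09.

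**4. What the AIC rule does.** Residual covariances were simulated with 91 df (100 patients − 8 centers − 1 for treatment), 200,000 trials per correlation. The REML likelihood ratio is 91 × ln[(v² − c²)/(s11·s22 − c²)], where s11 and s22 are the two sample variances, v is their mean and c is the sample covariance. Compound symmetry wins when this is below 2. It is picked in 43%, 37% and 25% of trials at correlation 0.3, 0.5 and 0.7.

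Both structures were then applied to those same trials:

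| In trials where compound symmetry is picked | Compound symmetry | Unstructured |
|---|---|---|
| One-sided error, 0 h | 6.3-6.6% | 5.7-6.0% |
| One-sided error, 24 h | 3.7-3.9% | 4.3-4.4% |
| Power at 24 h for 70 mmHg | about 88% | about 89% |

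Using compound symmetry there makes the SE about 3% smaller at 0 h and 3-4% larger at 24 h. This is less than in step 3 because AIC picks compound symmetry only when the sample SDs happen to look alike.

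**5. The whole procedure.** Averaged over all trials, one-sided error is about 5.2% at 0 h and 4.7-4.9% at 24 h. Power at 24 h is 90.1-90.3%, against 90.6% with unstructured fixed, a loss of about 0.3-0.5 points.

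**6. Two limiting cases.** If the true SDs are equal, compound symmetry is picked in about 84% of trials and one-sided error stays at about 5%. If the model is fitted exactly as listed, without time-by-treatment, it has one common treatment effect. When compound symmetry is picked, its SE then differs from the unstructured one by about 0.5%, with error of 5.0-5.2%.

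**The case against.** A mechanical, prespecified AIC rule is a legitimate choice, and SAP 9.5.1 describes the study as not pivotal. As a whole, the procedure stays close to nominal, and at 24 h it errs on the conservative side with power well above the planned 81%. The planning SDs come from one historical database, so they make unequal SDs likely in this trial but do not prove them. All of this stands, and it limits the point to a small one.

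Three stronger readings are tempting and should not be drawn.

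- **That the standard errors are wrong whenever compound symmetry is picked.** This needs the trial's SDs to differ and the model to contain time-by-treatment.
- **That compound symmetry causes the whole departure from 5%, or a power drop from about 91% to 88%.** More than half of that departure is also present under unstructured in the same trials, because they are selected for having similar sample SDs. The 91% is the figure for all trials; within the selected trials the cost is about 1 point.
- **That the revision history shows the rule is still faulty.** SAP 1.3 records that "The selection criterion has been changed to the matrix with the lowest value for the Akaike's Information Criterion". That corrects superseded text, and the current rule points the right way.

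The case for leaving the rule alone does not identify any benefit from the selection step. Its only gain is one covariance parameter, with about 100 patients.

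**Conclusion.** The point holds as a small improvement. The three-way selection reduces to one question, whether the SDs at 0 h and 24 h are forced equal, and the protocol's own planning data argue against forcing it. Under SDs of 137 and 117 mmHg, assumed correlations of 0.3 to 0.7, complete data and a time-by-treatment term, the selection step moves one-sided error by a few tenths of a point at each time and costs less than one point of 24 h power. It does not threaten the trial's conclusions.

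The size depends on a term that the SAP implies but does not list. Least squares means for each time and treatment, and a treatment effect within each time, need time-by-treatment. Without it the model returns the same difference at both times, and the covariance choice hardly matters. That omission matters more than the choice of matrix and should be settled in the same edit.

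**What to change.** In SAP 9.5.1, state that the within-patient covariance is unstructured and delete the three-model AIC selection. Keep compound symmetry only as a stated fallback if the unstructured model does not converge. Add time-by-treatment to the listed fixed effects and to the table shell in SAP 13. In SAP 1.2, record the move from the protocol's separate ANOVAs to a repeated measurements model.

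SAP 9.5.2.1 applies the primary method to 48 and 72 h, so the same wording carries over. The documents give no SDs for those times, so no size can be attached there.

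The cost is a few sentences before database lock and one covariance parameter. No change to data collection or sample size is needed, and the time-specific variances of the protocol's analysis are restored.

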3. OVERALL STUDY DESIGN AND PLAN DESCRIPTION

3.1. STUDY DESIGN

The study will be a phase 2, multi-center, randomized, double-blind, placebo-controlled, parallel-group (two arms) study.

It will involve 100 lung transplant recipients, randomly assigned in a 1:1 ratio to receive repertaxin or placebo, by continuous i.v. infusion for a period of 48 hours starting approximately 2 hours before reperfusion of the (first) transplanted lung occurs. The experimental treatment will be additional to the standard treatment of lung transplant recipients.

Recruitment will be competitive among the study sites, until the planned number of patients is enrolled. Competitive recruitment has been chosen to increase the speed of recruitment and to account for any difference in transplant rate among study sites.

Each patient will be involved in the study for 48 hour treatment, for measurements up to hospital discharge, and then for three visits (@ 1, 6, and 12 months post-transplant).

The double-blind will be maintained for the main part of the study only, i.e. up to the 1 month (at least 30 days post-transplant) follow-up visit of the last patient in. After database lock the randomization code will be broken and the results of the blind phase will be analyzed and the study will proceed in an open fashion.

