9.2. RANDOMIZATION

Patient will be randomized in a 1:1 fashion to either repertaxin or placebo. Treatment will be balanced within centers.

A master randomization list will be prepared, randomizing an excess of patients to allow flexible/competitive recruitment within each center. The randomization list will be prepared by **PPD** according to the current version of the Standard Operating procedure (SOP).

The randomization code will be broken at completion of the main part of the study, i.e. when the last patient in has completed his/her 30 days follow-up visit, and once the database has been locked.

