### 3.3 Randomization

Prior to surgery, patients who meet all the entry criteria and who provide written informed consent will be randomized to receive either repertaxin or placebo according to a 1:1 randomization.

A master randomization list was prepared for 352 patients (44 at each of 8 centers) by Insight Statistical Consulting on behalf of PPD. A dummy randomization was reviewed by statisticians at both PPD and Dompé prior to production of the final version. Since each patient should only ever require a single drug pack, the randomization number is identical to the patient number.

The randomization number is assigned sequentially at each site as patients are found to be eligible for entry to the study and are enrolled. Patients who are enrolled to replace patients who withdraw from the study prior to study drug infusion or lung transplantation will be issued a new randomization/patient number.

If a patient is allocated a randomization number and either the transplant does not happen or the study drug is not administered, the relevant drug box should be annulled to avoid its re-use with another patient.

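### A 10%-level treatment-by-center pre-test selects the primary model, and the plan does not say which contrast gives the primary p-value if the interaction is kept

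*SAP*

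**What the plan says.** SAP 9.5.1 (Primary analysis) fits a repeated measurements model with center, time point and treatment, and examines the treatment-by-center interaction: "if the term is not significant at the 10% level, it will be excluded from subsequent models". It continues: "The adjusted least squares means will be estimated for each combination of time point and treatment", and "The treatment effect within each time point will be compared using a one sided test at the 5% level". No center weights are given for the least squares means. Where center-by-treatment cells are too sparse for estimation, "centers will be pooled based on similar surgical practices"; no size threshold is stated. The shell for Tables 2.1.x and 2.2.x in SAP 13 has a center-by-treatment row beside the least squares means.

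Protocol 9.4.2 has the same 10% pre-test but a different consequence: "If a center by treatment interaction is detected, alternative methods of presentation will be explored". SAP 1.2 declares no changes from the protocol. Protocol 9.4.3 and SAP 9.5.2.1 carry the approach to 48 and 72 hours.

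On centers, protocol 3.1 says "Recruitment will be competitive among the study sites, until the planned number of patients is enrolled" and protocol 9.2 says "Treatment will be balanced within centers". SAP 3.3 describes a list for 8 centers with 44 numbers each, for a trial of 100 patients. Expected or actual center sizes are not given.

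**The concern.** The primary p-value can come from either of two models, and the data choose between them. One branch is defined: without the interaction there is a single additive treatment effect. The other is not. Once a treatment-by-center term is in the model, the overall treatment difference depends on how centers are weighted, and neither document states the weights.

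The gap would be filled late. The interaction test needs the true treatment codes, and SAP 8.2 has the pre-lock review run on a dummy randomization, with unblinding after lock. The contrast would therefore be settled with unblinded data in hand.

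If the equal-weight contrast is used, a center with a handful of patients counts as much as the largest one. That contrast equals the additive one plus a combination of the interaction estimates, and the pre-test picks out the trials where those estimates are large. Its ordinary t-test is then no longer at its nominal level in the selected trials.

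**Working it through.** **Inputs from the documents.** 50 per arm, SD 137 mmHg, one-sided alpha 0.05, difference 70 mmHg (SAP 3.2); interaction level 0.10 (SAP 9.5.1); 8 centers (SAP 3.3); arms balanced within center (protocol 9.2).

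**Assumed.** Center sizes, and equal center weights when the interaction is kept.

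**The plan's own figure.** A two-group t-test with 98 df (noncentral t) gives 81.4% power at 70 mmHg and 56.6% at 50 mmHg, against the stated 81% and 56%. Reproduced.

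**Standard errors.** With arms balanced in each of K centers of size n_k:

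- Additive model: SE = σ√(4/N) = 137 × √(4/100) = 27.4 mmHg.
- Equal-weight contrast: SE = (σ/K)√(Σ 4/n_k).

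Examples:

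- Sizes 26, 20, 16, 12, 10, 8, 4, 4: Σ1/n_k = 0.959, SE = (137/8) × √3.837 = 33.5, ratio 33.5/27.4 = 1.22.
- Sizes 40, 24, 12, 8, 6, 4, 4, 2: Σ1/n_k = 1.442, SE = (137/8) × √5.767 = 41.1, ratio 1.50.
- Sizes 40, 20, 14, 10, 8, 4, 2, 2: Σ1/n_k = 1.621, SE = (137/8) × √6.486 = 43.6, ratio 1.59.

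**Simulation of the two-step rule.** Normal data, one time point, no true interaction. The interaction F-test is run at 10%; if significant, the equal-weight contrast is tested, otherwise the additive one. For most layouts there were 600,000 null trials and 100,000 at 70 mmHg. The term was kept in 9.9% to 10.1% of null trials.

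| Assumed layout | SE ratio | Type I error given a switch | Overall type I error | Overall power, 70 mmHg |
|---|---|---|---|---|
| 8 near-equal centers | 1.00 | 5.7% | 5.05% | 81.4% |
| 24 down to 4 | 1.15 | 8.1% | 5.3% | 80.3% |
| 26 down to 4 | 1.22 | about 8.9% | 5.4% | not tabulated |
| 34 down to 4 | 1.32 | 9.7% | 5.5% | 79.3% |
| 40 down to 2 | 1.50 | 10.9% | 5.6% | 78.7% |
| Pooled to 5 centers | 1.07 | 7.1% | 5.25% | 80.9% |

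A more skewed layout in the 40-to-2 range (ratio about 1.6) takes overall type I error to about 5.7% and power to about 78%.

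**Comparator.** The additive model used throughout gives 5.0% type I error and about 81% power in every layout. In the switched trials themselves its error stays at 4.9% to 5.1%, so the excess comes from the change of contrast.

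**Check on the overall figures.** Overall = P(no switch) × rate + P(switch) × rate given a switch. For 40 down to 2:

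- Type I error: 0.9005 × 5.01% + 0.0995 × 10.91% = 4.51% + 1.09% = 5.60%.
- Power: 0.8997 × 81.44% + 0.1003 × 54.3% = 73.27% + 5.45% = 78.7%.

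**Two time points.** The planned model has two measurements per patient. A compound-symmetry version with assumed correlations of 0.3, 0.5 and 0.7 (400,000 trials each) gives, at 24 hours, 5.4% to 10.5% error given a switch and 5.0% to 5.5% overall. Missing 24-hour values were not modelled.

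**The case against.** The strongest reply is that this hardly matters. SAP 9.5.1 calls the study non-pivotal and accepts two unadjusted time points, so an overall excess of 0.1 to 0.7 percentage points would rarely change a decision. That stands, and it is why the point is minor.

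Second, the equal-weight contrast is not in the text. A reader might infer that the plan prescribes an unweighted average over centers. It does not: SAP 9.5.1 says only that least squares means will be adjusted. The defect that can be read off the page is the missing definition; the error rates above illustrate one likely way of filling it.

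Third, protocol 9.4.2 can be read as leaving the primary test alone and changing only the presentation. With SAP 1.2 declaring no departures, an automatic switch of the primary test is one reading and not the only one. That the two texts allow different readings is itself a reason to settle the matter.

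Fourth, a reader might take it as fact that centers will be very unequal. Competitive recruitment makes imbalance likely, but no sizes are given, and with near-equal centers the SE ratio is 1.00. The SAP's pooling rule would also remove the smallest centers, which drive the larger ratios. It softens the effect without fixing it: there is no size threshold, and its trigger, sparse center-by-treatment cells, is a condition the interaction term imposes. An additive model does not need every cell filled.

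**Conclusion.** The point holds as a gap in specification with a small numerical consequence. A 10%-level pre-test chooses the model behind the primary p-value, it fires by chance in about one trial in ten, and the contrast that then applies is undefined. If equal center weights are used, error in the switched trials is about 6% to 11% and the standard error 1.0 to about 1.6 times the additive one.

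A reader might infer from those conditional figures that the trial's false-positive rate is seriously inflated. It is not: over the layouts tried, overall type I error is about 5.1% to 5.7% against 5.0%, and the power loss is at most about 3 points. All of this rests on assumed center sizes and assumed equal weighting. It is a cheap improvement worth making and no threat to the trial's conclusions.

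**What to change.** In SAP 9.5.1, state that the primary contrast comes from the model without treatment-by-center interaction, whatever the interaction test shows. Report the interaction test and the by-center differences as exploratory, with the center weights stated for any averaged contrast. Pool centers only if a center main effect cannot be estimated.

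Apply the same rule to the sensitivity repeats, to the 48- and 72-hour analyses (SAP 9.5.2.1, protocol 9.4.3) and to the shell for Tables 2.1.x and 2.2.x, where the center-by-treatment row should move to the exploratory output. Then either align protocol 9.4.2 or declare the change in SAP 1.2.

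The cost is a few sentences in the SAP and the matching protocol text or declaration. SAP 1.1 has the plan finalized before database lock, so the change can be made blind. The downside is that real heterogeneity between centers would be reported outside the primary test, and the primary estimate would then be an average that gives larger centers more weight.
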